present the odds ratio, 95% confidence interval, and p-value to show whether there is a difference in rate of use of OAC at one year post intervention between the early intervention and delayed intervention groups. Similarly, we will analyze the proportion of days covered with an OAC prescription fill over the course of the follow-up. Patients will only be included in this analysis, if they had a prescription fill for apixaban, dabigatran, edoxaban, rivaroxaban, or warfarin.

Event rates for the following secondary outcomes will be summarized by treatment group, as defined by claims data:

- Stroke or TIA
- Ischemic stroke or unknown stroke
- Hemorrhagic stroke
- Hospitalization for any bleeding
- Composite of ischemic or hemorrhagic stroke
- Composite of ischemic stroke, hemorrhagic stroke, and hospitalization for any bleeding

For time-to-event outcomes, Kaplan-Meier cumulative incidence estimates and log-rank test will be utilized. ³⁹ In addition, Cox proportional hazards model with early intervention vs. delayed intervention as main effect will be used to assess the clinical outcomes, after adjusting for baseline risk factors. ⁴⁰ A robust sandwich covariance estimate or a frailty model will be used to account for effect of Data Partner. The hazard ratio, 95% confidence interval and p-value will be presented to summarize the difference in the risk of clinical outcome between early intervention and delayed intervention group. Inhospital death or medically attended death will be collected through claims data. Analyses will be performed using SAS software version 9.4 or higher (SAS Institute, Inc., Cary, NC).

More details on the statistical methods and analyses will be provided in the SAP. The SAP will be finalized prior to study database lock, 12 months after at least 80% of the early intervention mailings. Of note, all patient-level data will be maintained by the Data Partners, so analyses are expected to be conducted via a distributed SAS programming code developed by the coordinating center and results are expected to be returned, by Data Partner, in aggregate to the coordinating center. Analyses will be examined by Data Partner and across Data Partners.

XVII. DISSEMINATION PLAN OVERVIEW

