- Health care utilization, reported as counts of number of health care utilization events (outpatient visits, days hospitalized, number of emergency department visits, etc.)

Depending on the review of preliminary data, the primary endpoint and some secondary endpoints may be examined separately by warfarin and novel OAC. This will be descriptive only and will not include formal statistical testing.

C. EXPLORATORY ENDPOINTS

We will evaluate the effect of the early and delayed education interventions on the primary and secondary endpoints once at least 80% of eligible study participants have at least 24 months of follow-up time (the early intervention includes mailing to the patient and provider while the delayed intervention, at approximately 12 months follow-up, only includes a provider mailing). Note that we may

¹ Data for out of hospital mortality are not available

not conduct these analyses if the results of the primary outcome are null in the 12-month follow-up assessment. Therefore, this statistical analysis plan does not include the details of analyses for a 24-month assessment.

D. DATA SOURCE

The data used for the study are claims data from the five participating sites, transformed into the Sentinel Common Data Model. At the time of analysis, the data available in the Sentinel Distributed Database (i.e., those approved and in use for Sentinel routine surveillance activities) will be used to assess the primary and secondary endpoints.

As background, the identification and creation of the study cohort was based on the claims data in the Sentinel Distributed Database plus linked “fresh” data (i.e., about 1 month old) for pharmacy claims and enrollment information. The target population for the study was those members enrolled in the sites who did not have evidence of an OAC medication dispensing in the 12 months prior to randomization; the fresh and production data ensured we identified those eligible for the trial. The data used for routine Sentinel activities are several months old – hence the need for certain “fresh” data – and the date of the last available claims varies by site.

E. PATIENT INCLUSION CRITERIA

All inclusion and exclusion criteria were determined by claims data. For entry into the study, the following criteria **MUST** be met at the date of randomization:

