All possible person-time will be used to assess participants’ outcomes. For the time-to-event analysis, patients will be censored from the analysis at the time of death, disenrollment from the health plan, loss of medical or pharmacy coverage, or change in eligibility for inclusion in research based on health plan membership.

[figure not shown]
Providers may have more than 1 patient in the study – either within the same arm or in both the early and delayed intervention arms. The frequency of this, when provider overlap can be identified, will be reported descriptively and it is expected to be a low proportion of whole population. Depending on the number of patients in this scenario, a sensitivity analysis may be considered to examine the effect.

There were a few variations in the implementation of the early intervention across the Data Partners due to pragmatic issues. The intervention per the protocol is targeted at both member and provider (i.e., the provider who gave most recent AF diagnosis). If the AF provider was a facility in the source data, the educational intervention was applied to the member only, unless the site chose an alternate provider. In the latter case, the intervention was sent to both the member and the alternate provider. The number of patients in each of these variations to the intended intervention will be reported.

A detailed Consort flow diagram will be provided showing the number of patients randomized to the early and delayed intervention groups, the numbers of subjects lost to follow up or excluded from analyses, and the number of subjects evaluable for the key study endpoints (Figure 1).¹

All analyses will be conducted using SAS version 9.4 or higher software (SAS Institute Inc., Cary, NC). However, version and modules to be used could vary from one Data Partner to another. All tests will be two-sided and a p-value of <0.05 will be considered statistically significant. No multiplicity adjustment will be made.

Figure 1. Consort Flow Diagram

A. METHODS FOR ANALYSIS IN DISTRIBUTED DATA NETWORKS

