The time to first OAC initiation, is defined by the first fill date for apixaban, dabigatran, edoxaban, rivaroxaban, or warfarin. If there was no prescription fill for these medications, but the patient had 4 or more INR tests or results documented over the study period, the date of the first INR measurement would be used for initiation of OAC. Cumulative incidence rates estimated using Kaplan-Meier product limit will be presented for early intervention and delayed intervention groups. A Cox proportional hazards¹¹ model with early intervention vs. delayed intervention as the main effect will be used to model the time to first OAC initiation, after adjusting for baseline risk factors listed in Appendix A Table A. Robust standard errors will be used to account for the correlation of responses among the patients from a same service provider. The proportional hazard assumption will be verified using cumulative sums of martingale residuals and the Kolmogorov-type Supremum test. The hazard ratio, 95% CI and p-value will be summarized for time to the endpoint. Each Data Partner will run the SAS program(s) distributed by HPHCI, developed with the statistical team at Duke DCC, to perform Cox regression model¹¹ on their cohort of patients and return the estimated hazard ratio, 95% CI and p-value, shown in Table 3 in Appendix A (there will be one for each Data Partner), to HPHCI. Meta-analysis methods with inverse-variance weighting on log scale will be used to integrate the results and obtain the overall estimate of the hazard ratio, 95% CI and p-value for the entire study population.

There are patients for whom a provider was not identified, and therefore the provider letters were not mailed out. The primary endpoint will be summarized using frequencies and percentages and compared using Chi-Square test between the patients with provider letter and the patients without provider letter among those in the early intervention group. Each Data Partner will return the descriptive data, shown in Table 4 in Appendix A to HPHCI. Similar summary table will be generated for entire intervention arm by HPHCI.

2. OAC Adherence

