The proportion of patients actively on OAC at the end of follow-up will be summarized and compared between the early intervention and delayed intervention arms. Last Observation Carried Forward will be used if the patient is censored. To evaluate whether the early patient-level and provider-level educational intervention increases the proportion of patients being actively on OAC at the end of follow-up, we will calculate the odds ratio (i.e., the odds of an average patient in the early intervention group being actively on OAC at the end of follow-up as compared to the odds of an average patient in the delayed intervention group being actively on OAC at the end of follow-up) using logistic regression model adjusted for baseline risk factors listed in Appendix A Table A, with GEE to account for the correlation of responses among the patients from a same service provider. The odds ratio, 95% confidence interval (CI) and p-value will be presented to show whether there is a statistically significant difference in the proportion of patients who are actively on OAC at the end of follow-up between the early intervention and delayed intervention groups. Each Data Partner will run the SAS program(s) distributed by HPHCI, developed with the statistical team at Duke DCC, to perform logistic regression analysis on their cohort of patients and return the parameter estimate (SE), estimated odds ratio, 95% confidence interval (CI) and p-value, shown in Table 6 in Appendix A (there will be one for each Data Partner), to HPHCI. Meta-analysis methods with inverse-variance weighting on log scale will be used to integrate the results and obtain the estimate of the overall odds ratio, 95% confidence interval and p-value for entire study population.

4. Clinical Outcomes

Claims data (ICD-10-CM codes used for defining these outcomes are listed in Appendix C) will be used to define the following clinical outcomes:

- Hospitalization for ischemic stroke or unknown stroke
- Hospitalization for TIA
- Hospitalization for systemic embolism
- Hospitalization for ischemic stroke, TIA or systemic embolism
- Hospitalization for hemorrhagic stroke
- Hospitalization for any bleeding
- Hospitalization for ischemic or hemorrhagic stroke
- Hospitalization for ischemic or hemorrhagic stroke or systemic embolism
- Composite of ischemic stroke, hemorrhagic stroke, and hospitalization for any bleeding
- All-cause in-hospital death

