For each of these outcomes, time-to-event survival methodology will be implemented. Kaplan-Meier estimator¹² will be used to estimate the cumulative incidence rate during all follow-up and the log-rank test¹³ will be used to compare the survival curves. The Cox proportional hazards model with early intervention vs. delayed intervention as main effect will be used to model the time to event, after adjusting for baseline risk factors listed in Appendix A Table A. The hazard ratio, 95% CI and p-value will be presented to summarize the difference in the risk of clinical outcome between early intervention and delayed intervention groups. In-hospital death or medically attended death will be collected through claims data.

Each Data Partner will run SAS program(s) distributed by HPHCI, developed with the statistical team at Duke DCC, to perform analysis on their cohort of patients and return the results to HPHCI. For the comparison of cumulative incidence, each Data Partner will return the estimate of cumulative

occurrence and 95% CI by early intervention vs. delayed intervention, and p-value, as shown in Table 7 in Appendix A (there will be one for each Data Partner). For the comparison of risk, each Data Partner will return the parameter estimate (SE), hazard ratio, 95% CI and p-value, as shown in in Appendix A Table 8 (there will be one for each Data Partner). The statistical team will use meta-analysis methods to integrate the results and obtain the results for entire study population.

5. Health Care Utilization

The total counts of health care utilization (number of outpatient visits, emergency department visits, hospital admissions, and days hospitalized) at the end of follow-up time, including AF and non-AF related care, will be summarized by early intervention and delayed intervention group, as shown in Table 9 in Appendix A.

III. REFERENCES

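### Kaplan-Meier with death censored is reported as cumulative incidence in SAP Tables 3 and 7, which modestly overstates the arm-level percentages but not the arm comparisons

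*SAP*

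**What the plan says.** The general censoring rule for time-to-event outcomes is in SAP II: "patients will be censored from the analysis at the time of death, disenrollment from the health plan, loss of medical or pharmacy coverage", among other reasons. Protocol XIV.B has the same rule.

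For OAC start, SAP II.D.1 states: "Cumulative incidence rates estimated using Kaplan-Meier product limit will be presented for early intervention and delayed intervention groups". These figures go into Table 3, at 365 days. For the clinical outcomes, SAP II.D.4 says that the Kaplan-Meier estimator "will be used to estimate the cumulative incidence rate during all follow-up". These go into Table 7 with 95% confidence intervals, beside crude n/N. Protocol XVI.C agrees: "Kaplan-Meier cumulative incidence estimates and log-rank test will be utilized".

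On the recording of death, SAP II.D.4 says: "In-hospital death or medically attended death will be collected through claims data". It also lists "All-cause in-hospital death" as an outcome with its own time-to-event analysis. A footnote to SAP I.B adds: "Data for out of hospital mortality are not available".

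Neither document mentions competing risks, or says that the target is the risk in a hypothetical setting without deaths.

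**The concern.** A patient who has died cannot later fill a prescription or be admitted for stroke. Kaplan-Meier with that patient censored assumes that he or she would have gone on to have the event at the survivors' rate. With any deaths at all, one minus Kaplan-Meier is therefore higher than the proportion who actually have the event, which is what a column headed cumulative incidence is read to mean. The direction is certain. The size depends on mortality and grows with follow-up, and Table 7 covers all follow-up.

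The stake is the accuracy of the absolute percentages printed for each arm. Part of the error can be avoided: captured deaths must already be dated, because in-hospital death is itself analysed as a time to event.

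**Working it through.** **The plan's own event rates.** The one-year planning values in SAP I.G are 33% OAC start, 14.4% stroke or TIA, and 4.2% stroke, all for the delayed arm. As a check on them, the unrounded stroke or TIA rate is 0.33 × 7% + 0.67 × 18% = 14.37%. With 40,000 × (1 − 0.30) = 28,000 per arm and two-sided 0.05, a two-proportion test of 14.37% against 13.82% has 46.4% power (stated: 46%). Against 13.54% it has 80.9% (stated: 80%). The inputs reproduce. No stated figure is in dispute.

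**Assumptions.** Hazards are constant. The planning values are taken as what Kaplan-Meier would print. Mortality is not given. Captured deaths are assumed at 2-3% per year, and total mortality is varied more widely below.

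**Formulas.** For one-year event risk p and one-year death risk d:

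- event hazard l = −ln(1 − p); death hazard m = −ln(1 − d)
- Kaplan-Meier, death censored: 1 − exp(−l·t)
- cumulative incidence, death competing: [l/(l + m)] × [1 − exp(−(l + m)·t)]

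**Worked case, OAC start, d = 2%, t = 1.** l = 0.4005, m = 0.0202. Cumulative incidence = (0.4005/0.4207) × (1 − 0.67 × 0.98) = 0.952 × 0.3434 = 32.7%, against 33.0%.

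**One year, captured deaths competing:**

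| Outcome | Kaplan-Meier | d = 2% | d = 3% |
|---|---|---|---|
| OAC start | 33.0% | 32.7% | 32.5% |
| Stroke or TIA | 14.4% | 14.26% | 14.19% |
| Stroke | 4.2% | 4.16% | 4.14% |
| Bleeding (6% assumed; no rate given) | 6.0% | 5.94% | 5.91% |

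The relative overstatement is about 1.0% at d = 2% and 1.4-1.5% at d = 3%.

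**Longer follow-up.** SAP I.F expects more than 12 months for most patients. At an assumed 18 months and d = 2-3%, stroke goes from 6.23% to 6.14-6.09%, and stroke or TIA from 20.8% to 20.5-20.4%. The relative overstatement is about 1.5-2.3%.

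**What remains after the fix.** If total mortality were 10% per year and 30-50% of deaths were captured, one-year OAC start would move from 33.0% to 32.5-32.2%, whereas the full correction would give 31.4%. Stroke or TIA would move from 14.4% to 14.2-14.0% (full correction 13.7%). At 5% total mortality the OAC figures are 32.8-32.6% (full 32.2%). In these cases at least half of the overstatement stays.

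**Arm differences.** With equal mortality of 2% in both arms, the OAC difference (38% against 33%) goes from 5.00 to 4.96 points, and the stroke difference (3.7% against 4.2%) from 0.50 to 0.495. At 10% they are 4.79 and 0.475.

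**The case against.** The strongest reply is that nothing inferential turns on this. The primary analysis is adjusted logistic regression on a binary endpoint. Log-rank and Cox analyses with death censored are valid comparisons of cause-specific hazards. Table 7 also gives crude n/N, and Table 2a gives it for OAC start, so Kaplan-Meier is not the only absolute figure, although crude proportions have their own weakness when patients disenroll. All of this stands.

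The removable shift is also small against sampling error. From 1.96 × √(p(1 − p)/n) with 40,000 to 28,000 per arm, the confidence interval half-width is about 0.46-0.55 points for OAC start, 0.34-0.41 for stroke or TIA and 0.20-0.23 for stroke. The shifts above are about 0.3-0.5, 0.14-0.21 and 0.04-0.06 points. This stands as a limit on importance. It does not make the estimator right, since bias does not shrink with sample size.

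A further reply is that counting only captured deaths gives a mixed quantity that depends on where patients die. That is true, and it makes the correction partial. It does not make the change a matter of taste, because each death moved from censored to competing brings the estimate closer to the actual cumulative incidence.

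A reader might infer three stronger things that the documents do not support:

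- That the intervention effect or the primary result is overstated. The primary endpoint does not use Kaplan-Meier, and the arm differences barely move.
- That the printed confidence intervals will miss the true percentages. At 10% total mortality the OAC bias would be 1.6 points, above the half-width, but that rests wholly on an assumed mortality.
- That a competing-risk estimator would remove the bias. Out-of-hospital deaths are not available, so it cannot.

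**Conclusion.** The point holds as a modest correction to reported percentages. Tables 3 and 7 label as cumulative incidence a quantity that exceeds it whenever patients die. Under assumed captured mortality of 2-3% per year, the part that the trial's own data can remove is about 1-1.5% in relative terms at one year, and more over longer follow-up. Uncaptured deaths leave a residue that may be larger. The direction is certain. The size rests on constant hazards and on mortality rates that neither document states; at 2-15% total mortality the relative overstatement at one year runs from about 1% to 8%. No test, hazard ratio or conclusion is affected. The change is worth making because it is cheap, but it is of low priority.

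**What to change.** - In SAP II.D.1 and II.D.4, for OAC start and all clinical outcomes other than in-hospital death, replace Kaplan-Meier with the Aalen-Johansen estimator. The competing event should be every captured death, in-hospital or medically attended. Apply it at each Data Partner and in the pooled results.
- State that an admission for the event that ends in death counts as the event.
- Keep the log-rank tests (including the Table 7 p-value) and the Cox models, and describe them as cause-specific comparisons.
- Bring Protocol XVI.C into line.
- Footnote Tables 3 and 7: out-of-hospital deaths are not available and remain censored, so the figures are still slightly high.
- For in-hospital death, the competing event is out-of-hospital death, which is not observed. No change of estimator helps there; the footnote should cover it.

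If the sponsor prefers to keep Kaplan-Meier, the minimum is to relabel the columns and state that death was censored.

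Cost: SAP and protocol wording and a small change to the distributed SAS code. SAP II notes that software version and modules may vary between Data Partners, so the change needs testing at each. No new data are required. The downside is that the correction is only partial.

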Because the Sentinel Distributed Database will be used for analyses, and this information is refreshed approximately quarterly on different timetables for the different health plans, it is likely that when the required follow-up time is available for at least 80% of patients, there will be more than 12 months of follow-up for over 80% of patients. All participants' outcomes will be assessed using all possible person-time; patients will have different duration of follow-up and that will be accounted for in the analyses. Note that if the 24-month analysis is conducted, we will do that when at least 80% of members have at least 24 months of follow-up time.

A schematic diagram below shows the design of the early intervention period of the study: over the course of the follow-up, through the date on which at least 80% of eligible study participants have at least 12 months of follow-up time (see the protocol for the full study design and details):

[figure not shown]

*Baseline characteristics of delayed and early intervention cohorts will be taken from the same time point at randomization from a dataset that is archived at randomization, while exclusion criteria for evidence of OAC medication fill or P2Y12 antagonist use was determined at randomization for the early intervention cohort and approximately 12 months post-randomization for the delayed intervention cohort.

**All possible person-time will be used to assess participants' outcomes (patients will have different duration of follow-up).

For analysis, treatment status is at time of randomization or corresponding early intervention mailing; for the delayed intervention mailing it is prior to mailing.

A schematic diagram below shows the design of the delayed intervention portion of the study:

*All possible person-time will be used to assess participants' outcomes (patients will have different duration of follow-up).

For analysis, treatment status is at time of randomization or corresponding early intervention mailing; for the delayed intervention mailing it is prior to mailing.

[figure not shown]
G. SAMPLE SIZE JUSTIFICATION

1. Primary Endpoint

The following assumptions were used to determine the sample size and power for the primary endpoint assessing the proportion of AF patients with evidence of at least one OAC prescription fill through the date on which at least 80% of eligible study participants have at least 12 months of follow-up time:

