All primary analyses will be based on modified intention-to-treat (mITT) principle (i.e., all identified early intervention patients who met eligibility and were mailed the intervention will be included; using “pseudo” wave assignments, all identified delayed intervention patients who met eligibility at the time of corresponding early mailings will be included). Since the additional exclusions after randomization will be applied in the same way, using the same time points for both the early and delayed intervention groups, we expect there will be no effect from these additional exclusions on the randomization. The mITT analysis will include the following:

- Early intervention members who were mailed a letter, with follow-up beginning on the date of mailing (up to two dates per site and the dates varied by site).
- Delayed intervention members who were not on treatment at the date of mailing (wave assignments were made for the delayed as described earlier in section I.F) with follow-up beginning on that date.

An as-randomized analysis will be performed for an incident occurrence of the primary endpoint as a sensitivity analysis (using a washout of 365 days). Randomization occurred prior to treatment status assessment per the study design. Therefore, the as-randomized analysis will include people who were on treatment as well as others who were not truly eligible for the study (e.g., had incomplete or invalid addresses or had a “do not contact” status).

Potential sensitivity analysis for mITT analysis: There may be differential loss to follow up between the early and delayed intervention groups because some members did not have valid mailing addresses, though we did not assess the addresses of the members in the delayed intervention arm at the time of early intervention mailings. It is not possible to retrospectively ascertain the address status of the delayed intervention group as of the date on which mailing would have occurred for that group. We can estimate the magnitude by referring to the early intervention group, and in the early intervention group, we can compare the baseline characteristics and experience of the individuals who had no valid address to those who do.

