	Hospitalization for ischemic or hemorrhagic stroke or systemic embolism					
	Hospitalization for any bleeding					
	Composite of ischemic stroke, hemorrhagic stroke, systemic embolism and hospitalization for any bleeding					
	All-cause in-hospital death [PDX flag not applicable]					

Kaplan Meier curves will be generated for analyses related to Table 7.

Table 8. Hazard ratio of each outcome: early intervention vs. delayed intervention in the modified intention to treat (mITT) analysis

With / without Principal Discharge Diagnosis (PDX) Flag	Outcomes	Early Intervention, n/N (%)	Delayed Intervention, n/N (%)	Parameter Estimate (SE)	Unadj. Hazard Ratio (95% CI)	Adj. Hazard Ratio (95% CI)	p-value for adjusted HR
Principal Discharge Diagnosis (PDX Flag) Only	Hospitalization for ischemic stroke or unknown stroke						

	Hospitalization for TIA						
	Hospitalization for systemic embolism						
	Hospitalization for ischemic stroke, TIA, or systemic embolism						
	Hospitalization for hemorrhagic stroke						
	Hospitalization for ischemic or hemorrhagic stroke						
	Hospitalization for ischemic or hemorrhagic stroke or systemic embolism						
	Hospitalization for any bleeding						
	Composite of ischemic stroke, hemorrhagic stroke, systemic embolism and hospitaliz						

	ation for any bleeding						
Ignore Principal Discharge Diagnosis (PDX) Flag	Hospitalization for ischemic stroke or unknown stroke						
	Hospitalization for TIA						
	Hospitalization for systemic embolism						
	Hospitalization for ischemic stroke, TIA, or systemic embolism						
	Hospitalization for hemorrhagic stroke						
	Hospitalization for ischemic or hemorrhagic stroke						
	Hospitalization for ischemic or hemorrhagic stroke or systemic embolism						
	Hospitalization for any bleeding						

	Composite of ischemic stroke, hemorrhagic stroke, systemic embolism and hospitalization for any bleeding						
	All-cause in-hospital death						

Kaplan Meier curves will be generated for analyses related to Table 8.

Clinical endpoints for Table 8 will be based only on diagnoses that are the principal discharge diagnoses.

Table 9. Health care utilization during all follow up time: early Intervention vs. delayed Intervention in the modified intention to treat (mITT) analysis

	Early Intervention	Delayed Intervention	p-value
Total patients	N =	N =	NA
Total encounters			
Total # of encounters per arm (N)			NA

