# with ≥1 encounter			
Mean			
Standard deviation			
Minimum			
Maximum			
Median (range across sites)			
Number of days hospitalized			
Mean			
Standard deviation			
Minimum			
Maximum			
Median (range across sites)			
Total # of days hospitalized per arm			NA

Table 1S. Baseline characteristics of all patients in the as-randomized analysis by early intervention vs. delayed intervention (sensitivity analysis)

	Overall (N=XXXX)	Early intervention (N=XXXX)	Delayed intervention (N=XXXX)	p-value	Stand. mean difference (%)
Demographics					
Age					
N					
Mean (SD)					
Median (Min, 25 th , 75 th , Max)					

	Overall (N=XXXX)	Early intervention (N=XXXX)	Delayed intervention (N=XXXX)	p-value	Stand. mean difference (%)
30-34 yr, %					
35-39, %					
40-44, %					
45-49, %					
50-54, %					
55-59, %					
60-64, %					
65-69, %					
70-74, %					
75-79, %					
≥ 80, %					
Sex					
N					
Female, %					
Region					
New England, %					
Mid-Atlantic, %					
South-Atlantic, %					
Midwest, %					
Mountain, %					
Pacific, %					
Unknown, %					
Medical history					
History of anemia?					
N					
Yes, %					
History of hypertension?					
N					
Yes, %					
History of diabetes?					
N					
Yes, %					
History of hospitalization for any bleeding?					
N					
Yes, %					
History of peripheral vascular disease?					
N					
Yes, %					
History of prior cerebrovascular disease?					
N					
Yes, %					

	Overall (N=XXXX)	Early intervention (N=XXXX)	Delayed intervention (N=XXXX)	p-value	Stand. mean difference (%)
History of heart failure?					
N					
Yes, %					
History of kidney disease?					
N					
Yes, %					
History of MI					
N					
Yes, %					
History of CABG					
N					
Yes, %					
History of coronary stent					
N					
Yes, %					
CHA ₂ DS ₂ VASc score					
N					
Mean (SD)					
Median (25th, 75th)					
0, %					
1, %					
2, %					
3, %					
4, %					
5, %					
6, %					
7, %					
8, %					
9, %					
Bleeding risk score: ATRIA score					
Low (≤ 3), %					
Intermediate (4), %					
High (≥ 5), %					
Hospitalization in the prior 6 months					
0, %					
1, %					
2, %					
≥ 3 , %					
Mean (SD) follow up time					
Minimum follow up time					
Maximum follow up time					
Median follow up time (range across sites)					

Table 2S. – Odds ratio of one OAC dispensing or 4 or more INRs (primary endpoint) over the course of the 12-months of follow-up: early intervention vs. delayed intervention – as-randomized analysis (sensitivity analysis)

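### Health care utilization is compared as counts over unequal follow-up, with a p-value column but no person-time denominator

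*SAP*

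**What the plan says.** SAP I.B lists this secondary endpoint last, as "Health care utilization, reported as counts of number of health care utilization events". Section II.D.5 gives it one sentence: counts of outpatient visits, emergency visits, admissions and hospital days "at the end of follow-up time, including AF and non-AF related care, will be summarized by early intervention and delayed intervention group", with a pointer to Appendix A.

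The shell there is captioned "Table 9. Health care utilization during all follow up time: early Intervention vs. delayed Intervention". For each encounter type it has rows for the arm total, the number of patients with at least one encounter, mean, SD, minimum, maximum and median. The hospital-days block ends with "Total # of days hospitalized per arm". Patient numbers per arm stand at the top. There is a p-value column, but neither the table nor II.D.5 names a test. Person-years, rates, an offset and a fixed counting window are all absent.

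Three other statements bear on this:

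- SAP I.F says that "patients will have different duration of follow-up and that will be accounted for in the analyses".
- SAP II defines the early part of the modified intention-to-treat set as "Early intervention members who were mailed a letter, with follow-up beginning on the date of mailing". Delayed-arm members enter if they are eligible and untreated at the corresponding mailing date. Their addresses were not checked.
- The same section warns: "There may be differential loss to follow up between the early and delayed intervention groups because some members did not have valid mailing addresses".

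**The concern.** A count accrued over all follow-up is the product of how often a patient uses care and how long the patient is observed. The SAP acknowledges that observation time varies and promises to deal with it. It does so for OAC initiation and the clinical outcomes (Kaplan-Meier and Cox, II.D.1 and II.D.4) and for adherence (proportion of days covered, II.D.2). For utilization it gives no mechanism, and Table A's list of adjusted analyses stops at II.D.4.

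At stake is the reading of a secondary endpoint. If one arm is followed longer on average, Table 9 would show more visits, more admissions and more patients with at least one encounter in that arm, even with identical rates of care. With about 80,000 patients, two-sided testing at 0.05 and no multiplicity adjustment, a small exposure difference could come out as statistically significant.

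**Working it through.** The documents state no utilization rate, SD or power, so there is no planned figure to reproduce. The check is structural, followed by an illustration.

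**Structure.** For an arm with N patients, true rate λ per year and mean follow-up F:

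- arm total = N × λ × F (depends on arm size and follow-up);
- mean per patient = λ × F (depends on follow-up only);
- events per person-year = N × λ × F / (N × F) = λ (depends on neither).

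Table 9 reports the first two and not the third.

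**Inputs.** From the documents: 30% one-year attrition and about 80,000 patients randomized 1:1, so about 40,000 per arm (SAP I.F and I.G). Assumed: any attrition gap between the arms and its direction, exponential loss, a 12-month horizon, 10 outpatient visits a year, an SD of 12 for the per-patient count, and all 40,000 per arm analyzed.

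**Formulas.** Mean follow-up with attrition a over one year is F = a / (−ln(1 − a)).

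- a = 0.30: 0.30 / 0.3567 = 0.8411 years
- a = 0.28: 0.28 / 0.3285 = 0.8523 years
- a = 0.27: 0.27 / 0.3147 = 0.8579 years
- a = 0.25: 0.25 / 0.2877 = 0.8690 years

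The standard error of the difference in means is sqrt(2 × 144 / 40,000) = 0.0849 visits. With equal true rates, z = 10 × (difference in F) / 0.0849.

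| Attrition, early vs delayed | Ratio of mean counts | z | Ratio of rates |
|---|---|---|---|
| 30% vs 30% | 1.000 | 0 | 1.000 |
| 28% vs 30% | 1.013 | 1.33 | 1.000 |
| 27% vs 30% | 1.020 | 1.98 | 1.000 |
| 25% vs 30% | 1.033 | 3.29 | 1.000 |

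The 27% line in full: 0.8579 / 0.8411 = 1.020, and 10 × 0.0168 / 0.0849 = 1.98. With SD 13 instead of 12, z falls to 1.83.

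**Second dropout model.** With uniform dropout, F = 1 − d/2. Attrition of 28% versus 32% gives 0.86 / 0.84 = 1.024. Taking a coefficient of variation of 1 to 2 and 20,000 to 40,000 patients per arm (all assumed), the chance of p < 0.05 with equal true rates is 22% to 91%. With equal attrition it is 5%.

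**Arm size.** If 5% of early patients were unmailed and dropped (assumed), the early total would be 0.95 of the delayed total, but the mean per patient would stay at a ratio of 1.00.

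**The case against.** The strongest reply is that nothing shows the arms will differ in follow-up. Randomization is 1:1 within each plan. Delayed patients start follow-up on the mailing dates of the same wave at the same Data Partner. Data refresh dates vary between plans, not between arms within a plan. Under SAP I.F, death, disenrollment or OAC start between randomization and mailing excludes patients in both arms. The warning about differential loss concerns invalid addresses and says only that it may occur. A link from a bad address to shorter follow-up after entry is inference. All of this stands: a reader might infer that follow-up does differ, and the documents support only that it may.

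A reader might also infer that a larger arm would appear to use more care. That holds only for the total rows, which are descriptive and printed with the number of patients. Two of them, all encounters and hospital days, already have the p-value marked NA; in the other blocks the cell for the total is blank. Means and medians do not scale with arm size.

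Two further replies stand in part. Table 1 reports follow-up time by arm, so an imbalance would be visible and a crude rate could be derived; but that would not correct Table 9's means or p-values. The Appendix A note covering Tables 2 through 9 speaks of model results and meta-analysis; but II.D.5 defines no model, and Table 9 has no column for an estimate.

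Finally, both documents define the endpoint as counts, and II.D.5 says only that they are summarized. A purely descriptive table would be defensible. The p-value column makes it a comparison.

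**Conclusion.** The point holds in a limited form. As written, the plan would test counts that depend on exposure, against its own statement that differing follow-up will be handled. Whether this produces bias depends on whether mean follow-up differs between the arms. The SAP concedes that possibility, and only the early arm is restricted to members who were mailed. If follow-up is balanced, the result is extra noise.

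The illustrated size is about 2.0% more encounters and z about 1.98 at 27% versus 30% attrition. Apart from the 30% attrition and the planned numbers, every input is assumed, and z falls below 1.96 with modest changes to them. The 12-month cap is also a simplification, since Table 9 counts all follow-up. The figures show what could happen and are not an expected bias.

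This is a secondary endpoint, and the primary result is unaffected.

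**What to change.** - Add person-years by arm to Table 9, and report each utilization type as events (or hospital days) per person-year. Totals and per-patient means can stay as description.
- Base any p-value on a rate ratio from a negative binomial or robust Poisson model with log follow-up time as offset. Fit it at each Data Partner and pool by inverse variance on the log scale, as the SAP already does for odds and hazard ratios.
- Give no p-value for raw counts.
- If no model is run, present the rates descriptively and remove the p-value column.

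The offset removes the effect of unequal observation time. It does not remove bias if patients who leave early also use care at a different rate, so follow-up by arm from Table 1 should be read alongside.

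The cost is one standard model per utilization type in the distributed program. Follow-up time is already computed for Table 1, so no new data are needed.
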